		signatures and date, as well as print/sign/scan the consent form and return the signed and dated consent to the study team; and describe how the study team will subsequently countersign, return the counter-signed copy to the subject for subjects' records; how subjects may maintain a copy of their signed consent; and how the study team will document and/or maintain a record of the executed consent form. • Updated consent to reflect how PI will be available for questions during the study.	
2	8/8/22	Will the participants names be on the electronic survey?	Yes- Child, Adolescent, and General Consent

		of clients with identified an mental health disorder. Is that accurate? Are you solely recruiting through flyers sent via email by staff and posted in the facility? I will not be asking anyone at Wolfson Children's Hospital for names of clients with identified mental health disorders. I will solely be recruiting through flyers sent via email and staff, posted flyers in the facility, and providers and staff have agreed to provide possible clients meeting the project criteria with the information for the study.	
3	8/10/22	Please change regarding the information below: Parents/legal guardians will be sent the survey via email before the adolescent is sent the survey. During the parent/legal guardian survey, they will be asked to provide assent for their adolescent to participate in the study and assent for HIPAA authorization for their adolescent. If parents/legal guardians do not provide assent for the study, the dyad will be removed from the study. Once parents/legal guardians provide assent and finish their survey, the survey will then be sent to the email address provided for the adolescent.	No-Clarification on the consenting/ assenting process. No change to consenting documents.

- To explain the process of consenting parents and obtaining assent from adolescents. For example:
 - o Parents can consent for their children to participate, but you still want to obtain child assent. So, when the parent/legal guardian are sent the survey, they will be asked to provide consent for their child to participate in the study. If the parent/legal guardian does not provide consent, the dyad will be removed from the study. Once parents/guardians provide consent, a survey will be sent to the email of the child and the child/adolescent will be asked to assent.
- Updating recruitment process to include posting approved study flyers on social media platforms. Including the Bridge program at Wolfson Childrens Hospital for study flyer placement.
- Updated estimated project timeline.
- Update Inclusion/Exclusion criteria. Modifications to exclusion/inclusion criteria include: "If pt scores <13 on WHO-5 criteria, they MUST currently be enrolled in therapy services to participate."
- Incentive change: A \$30.00 Amazon
 E-Gift Card will be emailed to each
 adolescent-parent dyad after
 completing the post-survey.

4	10/31/22	 Incentive change: A \$30.00 Amazon E-Gift Card will be emailed to the first 30 adolescent-parent dyads that complete the post-intervention survey (Change reflected on flyer). Adding statistician to project team. Goal Number of parent-adolescent dyads in study. Clarified zoom session meeting dates. Updated final question on the post-intervention survey to assess the impact of the moderator ([name]) on the receptiveness of the educational presentation (Reflected on updated questionnaires). 	
5	11/15/22		

Study Summary

Study Title	Promote Healthy Lifestyle Behaviors for Adolescents with Mental Health Conditions
Study Design	Quasi-experimental study with a one group pretest- posttest design
Primary Objective	To evaluate the impact of an online educational program on improving healthy lifestyle knowledge and behaviors (nutrition, physical activity, screen time, and sleep) among adolescents diagnosed with a mental health condition(s) and their parent(s)/ legal guardian(s).
Secondary Objective(s)	1. Educate adolescents with mental health conditions and their family members about ways to improve healthy lifestyle behaviors.
	2. Evaluate an increase in knowledge on healthy lifestyle behaviors after a 45-minute online education session.
	3. Evaluate an increase in healthy lifestyle behaviors after the intervention.
Research Intervention(s)/ Investigational Agent(s)	This project utilizes a one-group pretest-posttest design study for 30 (Goal) adolescents (aged 12-17 years) diagnosed with a mental health condition(s) and their parent(s)/legal guardian(s). This project will implement best practices to promote healthy lifestyle knowledge and behaviors to adolescents and their parent(s)/legal guardian(s). An online educational program will be delivered via a 45-minute Zoom meeting. We will compare the effects of an educational program on healthy lifestyle knowledge and behaviors pre-and post-program (after one month) via a REDCap survey for the adolescent and their parent/legal guardian. The survey will utilize an adapted version of the 2021 National Youth Risk Behavior Survey (YRBS) and the 2020 National Survey of Children's Health (NSCH-T3). The analysis of this project will compare changes in healthy lifestyle knowledge and using a paired t-test.
IND/IDE #	N/A

Study Population	 Adolescents, 12-17 years old, with a clinical diagnosis of a mental health condition(s) Adolescent's parent(s)/legal guardian(s) ages 18 or older
Sample Size	Goal: 30 adolescent-parent dyads
Study Duration for individual participants	One month
Study Specific Abbreviations/ Definitions	PA- Physical Activity

1.0 Objectives*

Purpose:

The purpose of this project is to improve healthy lifestyle knowledge and behaviors among adolescents with a mental health condition(s) through preventative and detailed nutritional, physical activity, screen time, and sleep education.

Clinical Question:

Among adolescents 12-17 years old who are diagnosed with a mental health condition(s), does an educational intervention improve healthy lifestyle knowledge and behaviors including nutrition, physical activity, screen time, and sleep?

Aims

We will accomplish three aims using a one group pretest-posttest design:

- 1. Educate adolescents with mental health conditions and their family members about ways to improve healthy lifestyle behaviors.
- 2. Evaluate an increase in knowledge on healthy lifestyle behaviors after a 45-minute online education session.
- 3. Evaluate an increase in healthy lifestyle behaviors after the intervention.

Background*

Background and Significance

The pediatric population faces a public health crisis involving children and adolescents with overweight or obesity. Childhood obesity has become the most disconcerting and predominant pediatric nutritional disorder worldwide (Centers for Disease Control and Prevention [CDC], 2020a). From 2017 to 2018, 19.3% of the children and adolescents in the United States (US) were diagnosed with obesity (CDC, 2020b). Childhood obesity has been linked to psychological conditions such as depression and anxiety (CDC, 2020b). Children that are overweight or obese are more commonly diagnosed with depression than children with a healthy weight (Lindberg et al., 2020). In 2019, 13.6% of children five to seventeen years old received mental health treatment in twelve months, and 8.4% of that population had taken psychotropic medication for their mental health condition (CDC, 2020c).

Healthy lifestyle behaviors impact short and long-term health and quality of life among children with depression. Physical activity (PA), healthy nutritional habits, and maintaining a healthy weight can improve children's quality of life with depression and overweight or obesity (Rippe, 2018). Parents have the most significant influence on their children's health. Thus, family-based intervention studies have been conducted to

promote children's healthy lifestyle behaviors. Behavioral interventions that combine nutritional, physical, and behavioral components and parental involvement have proven to be the best and most effective practice for treating and preventing childhood obesity among adolescents 12-17 years old (Al-Khudairy et al., 2017).

Although there is evidence to support that adolescents benefit from peer and family support and group education, there are few in-depth studies documenting lifestyle modifications that can improve this population's overall physical and mental health. Given this lack of implementation into practice, this project aims to improve healthy lifestyle knowledge and behaviors among adolescents with a mental health condition(s) through preventative and detailed nutritional, physical activity, screen time, and sleep education.

This study's purpose is to identify factors that may aid in answering the clinical question: Among adolescents 12-17 years old who are diagnosed with a mental health condition(s), does a family-based educational intervention improve healthy lifestyle knowledge and behaviors, including nutrition, PA, screen time, and sleep? The specific aims are to: Aim 1: To educate adolescents with mental health conditions and their family members about ways to improve healthy lifestyle behaviors. Aim 2: To evaluate an increase in knowledge on healthy lifestyle behaviors after a 45-minute online education session. Aim 3: To evaluate an increase in healthy lifestyle behaviors after the intervention.

Study Endpoints*

Study Endpoints*

This study will be completed by May 2023.

Study Intervention/Investigational Agent

1.1 Description:

This project utilizes a one-group pretest-posttest design study for 30 adolescents (aged 12-17 years) diagnosed with a mental health condition(s) and their parent/legal guardian. This project will implement best practices to promote healthy lifestyle knowledge and behaviors to adolescents and their parent(s)/legal guardian(s). This will be a 45-minute educational presentation delivered via Zoom. Participants can select between multiple dates/times (over a 3-week period) for the educational session. We will compare the effects of an educational program on healthy lifestyle knowledge and behaviors preand post-program (after one month) via a REDCap survey for the adolescent and their parent/legal guardian. The survey will utilize an adapted version of the 2021 National Youth Risk Behavior Survey (YRBS) and the 2020 National Survey of Children's Health (NSCH-T3). The analysis of this project will compare changes in healthy lifestyle knowledge and behaviors using a paired t-test. The educational presentation will be recorded and emailed to participants within 1 week of intervention to re-watch/review.

The educational program will promote a healthy lifestyle knowledge and behaviors through education established by the Centers for Disease Control and Prevention, the World Health Organization, and the American Academy of Pediatrics. Educational sessions will include the importance of healthy lifestyle modifications in the adolescent population with a mental health condition(s), lifestyle recommendations versus reality, nutrition, physical activity, screen time, and sleep recommendations and guidelines. The educational presentation via Zoom will include: 5-10 minutes of education regarding recommendations versus reality for nutrition, PA, screen time, and sleep, 20-25 minutes of education regarding ways to improve healthy lifestyle knowledge and behaviors. Potential obstacles to consider for this project include the recruitment of thirty applicants for this study and maintaining participant and family involvement in the study from pre-intervention to post-intervention.

- 1.2 Drug/Device Handling: N/A
- 1.3 N/A

Procedures Involved*

1.4 Describe and explain the study design.

Interventions will be evaluated through a pre- and post-intervention survey regarding parental/adolescent's healthy lifestyle knowledge and behaviors developed from nationally approved health surveys including the National Survey of Children's Health (NSCH), the WHO (Five) Well-Being Index, the Patient Health Questionnaire- 9 (PHQ-9), and the Youth Risk Behavior Surveillance System (YRBSS) (Bureau, n.d.; Kroenke et al., 2001; *CDC*, 2021; *WHO-5 Questionnaires*, n.d.). The World Health Organization (Five) Well-Being Index questions will appear in the REDCap survey as a screening prior to the project survey. This survey is suitable for children nine years and above. If the raw score is below 13 or if the patient has answered 0 to 1 to any of the five items, they will not be allowed to complete the REDCap survey or participate in the project (*The World Health Organisation- Five Well-Being Index (WHO-5)*, n.d.; World Health Organization. Regional Office for Europe, 1998).

The pre- and post-intervention survey will be the same, except the post-intervention survey will not include demographic questions. The adolescent survey will include 61 questions total: 6 WHO-5 mental health screening, 7 demographics, 2 weight/self-image, 16 nutrition, 10 PA, 12 sleep, 5 screen time, 4 home environment, and 1 comment box for questions regarding nutrition, PA, screen time, and sleep. The parent/legal guardian(s) survey will include 70 questions total: 4 adolescent mental health screening, 11 demographics, 7 evaluating adolescent overall health, 16 nutrition, 10 PA, 12 sleep, 5 screen time, 4 home environment, 1 comment box for questions regarding nutrition, PA, screen time, and sleep. 1 question will be added to the end of the post-intervention survey (for both adolescent and parent/legal guardian surveys) to assess the impact of the Zoom moderator on the educational intervention. See Appendix.

- 1.5 Provide a description of all research procedures being performed and when they are performed, including procedures being performed to monitor subjects for safety or minimize risks.
 - This project utilizes a one-group pretest-posttest design study for 30 adolescents (aged 12-17 years) diagnosed with a mental health condition(s) and their parent/legal guardian.
 - This will be an educational program delivered via a 45-minute presentation delivered via Zoom.
 - Participants can select between multiple dates/times (over a 3-week period) for educational session.
 - The educational presentation will be recorded and emailed to participants within 1 week of intervention to re-watch/review.
 - The educational program will promote a healthy lifestyle knowledge and behaviors through education evidenced by the CDC, WHO, and the American Academy of Pediatrics. Educational sessions will include the importance of healthy lifestyle modifications in the adolescent population with a mental health condition(s), lifestyle recommendations versus reality, nutrition, physical activity, screen time, and sleep recommendations and guidelines. The educational presentation will

- include: 5-10 minutes of education regarding recommendations versus reality for nutrition, PA, screen time, and sleep, 20-25 minutes of education regarding ways to improve healthy lifestyle knowledge and behaviors, 10 minutes for questions and discussion.
- We will compare the effects of an educational program on healthy lifestyle knowledge and behaviors pre-and post-program (after one month) via a REDCap survey for the adolescent and their parent/legal guardian.
 - O The survey will utilize an adapted version of the 2021 National Youth Risk Behavior Survey (YRBS) and the 2020 National Survey of Children's Health (NSCH-T3). The analysis of this project will compare changes in healthy lifestyle knowledge and behaviors and knowledge using a paired t-test.
- Information required for this study will be provided through the pre-and post-intervention survey.
- PHI will not be obtained from the EHR. The only PHI information for this study will be provided voluntarily through the REDCap survey.
 - a. The PHI information provided through REDCap includes:
 - i. Name of current mental health diagnoses
 - ii. Mental health diagnosis date
 - iii. Name of medications
 - iv. Date of birth
 - b. Participants names will not be on the electronic survey.
- 1.6 The pre- and post-intervention survey will be the same, except the post-intervention survey will not include demographic questions. The adolescent survey will include 61 questions total:6 WHO-5 mental health screening, 7 demographics, 2 weight/self-image, 16 nutrition, 10 PA, 12 sleep, 5 screen time, 4 home environment, and 1 comment box for questions regarding nutrition, PA, screen time, and sleep. The parent/legal guardian(s) survey will include 70 questions total: 4 adolescent mental health screening, 11 demographics, 7 evaluating adolescent overall health, 16 nutrition, 10 PA, 12 sleep, 5 screen time, 4 home environment, and 1 comment box for questions regarding nutrition, PA, screen time, and sleep. 1 question will be added to the end of the post-intervention survey (for both adolescent and parent/legal guardian surveys) to assess the impact of the Zoom moderator on the educational intervention.

1.7 Describe:

- Procedures performed to lessen the probability or magnitude of risks.
 - Parental Consent and Adolescent Assent
 - o Parental Involvement in educational intervention
 - Adolescent mental health screening- The World Health Organization (Five) Well-Being Index questions
 - a. If the raw score is below 13 or if the adolescent has answered 0 to 1 to any of the five items, they will not be allowed to complete the REDCap survey or participate in

the project, unless they are currently enrolled in outpatient mental health services (Ex: counseling, therapy, partial hospitalization).

- All drugs and devices used in the research and the purpose of their use, and their regulatory approval status. N/A
- The source records that will be used to collect data about subjects. (Attach all surveys, scripts, and data collection forms.)
 - See Appendix A and B
- 1.8 What data will be collected during the study and how that data will be obtained.
 - The data collected will compare the effects of an educational program on healthy lifestyle knowledge and behaviors pre-and post-program (after one month) via a REDCap survey for the adolescent and their parent/legal guardian.
 - The data will be obtained through a REDCap survey.

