1.9 N/A

Data and Specimen Banking* N/A

Sharing of Results with Subjects* N/A

Study Timelines*

1.10 Describe:

- Project recruitment will be begin in early October 2022.
- Project recruitment will end November 2022.
- Project pre-survey survey will be sent out the middle to end of November 2022.
- Participants will have 2 weeks to complete pre-survey prior to Zoom educational session. A reminder email will be sent to complete pre-survey.
- An online educational session will be held middle to end of November 2022. Participants can select between multiple dates/times (over a 3-week period) for educational session.
- Participants will be emailed the recorded educational presentation within 1 week of intervention.
- Participants will then receive a post-survey 1 month after educational session.
- Study will be completed by middle/end of December 2022-Early January 2023.
- The duration of an individual subject's participation in the study.
 - o 1 month duration
- The duration anticipated to enroll all study subjects.
 - o 1 month

- The estimated date for the investigators to complete this study (complete primary analyses)
 - Study will be completed by Middle/End of December 2022- Early January 2023

Inclusion and Exclusion Criteria*

- 1.11 Describe how individuals will be screened for eligibility.
 - Adolescents, 12-17 years old, with a clinical diagnosis of a mental health condition(s) and their parent/legal guardian.
 - Examples of eligible diagnosed mental health conditions include major depressive disorder (MDD), generalized anxiety disorder (GAD), attention-deficit disorder (ADD)/ attention deficit hyperactivity disorder (ADHD), bipolar disorder (BPD).
 - Adolescents that score below 13 on the World Health Organization (Five) Well-Being Index survey or if the adolescent has answered 0 to 1 to any of the five items, they will not be allowed to complete the REDCap survey or participate in the project unless they are currently enrolled in outpatient mental health services (Ex: counseling, therapy, partial hospitalization).

Parent(s)/legal guardian(s), 18 years old or order, live with adolescents diagnosed with mental health condition(s)

- 1.12 Describe the criteria that define who will be included or excluded in your final study sample.
 - Inclusion Criteria:
 - o Individuals who are not yet adults (Adolescents 12-17 years old)
 - With diagnosed mental health condition (ex: Depression, Anxiety, ADD/ADHD) more than one year ago.

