- c. Investigator accesses the informed consent form (ICF) to affirm informed consent, and e-signs their portion.
- d. Participant and investigator each keep a copy of ICF for their research.
- o For those who decline the study, REDCap will provide a message for those who decline.
 - a. The message as follows: Thank you for your interest. If you agree to participate in the future, please let us know. You can close this window or click on submit below."
 - b. They will still have the opportunity to download copy of informed consent.
 - c. A PDF copy of the e-Consent will be automatically saved in the project's file suppository (not in the record), which can be accessed and downloaded by authorized users as needed
 - d. E-Consent Framework will be enabled which:
 - i. Includes a certification page at the end of the survey
 - ii. Requires respondents to review and confirm information an inline PDF copy of the survey to be marked as complete.
 - iii. Allows versioning of a form.

Cognitively Impaired Adults N/A
Adults Unable to Consent N/A
Adults Unable to Consent N/A

Process to Document Consent in Writing Please check attached consents.

Setting

- 2.26 Describe the sites or locations where your research team will conduct the research.
 - Identify where your research team will identify and recruit potential subjects.
 - The setting will be the Intensive Outpatient Behavioral Health Program (IOP) the Partial Hospitalization Program (PHP) and Bridge Program at Wolfson Children's Hospital in Jacksonville, Florida.
 - Study flyers will be posted on various social media platforms.
 - *Identify where research procedures will be performed.*
 - Online via REDCap Survey and Zoom-based educational intervention.
 - Describe the composition and involvement of any community advisory board.
 N/A
 - For research conducted outside of the organization and its affiliates describe:
 - O Site-specific regulations or customs affecting the research for research outside the organization. N/A
 - Local scientific and ethical review structure outside the organization.

 N/A

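### The lesson recording is in participants' hands at the remote post-survey but not at the pre-survey, and the visible respondent wording does not ask for answers from memory, so look-up can inflate the measured knowledge gain (Aim 2)

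*Combined protocol and SAP*

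**What the plan says.** Aim 2 in section 1.0 is to "Evaluate an increase in knowledge on healthy lifestyle behaviors after a 45-minute online education session". Knowledge is also half of the primary objective in the Study Summary. Sections 1.1, 1.5 and 2.17 test change with a paired t-test.

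The sequence is set out in section 1.10 (Study Timelines):

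- Before the session: "Participants will have 2 weeks to complete pre-survey prior to Zoom educational session".
- After the session: "Participants will be emailed the recorded educational presentation within 1 week of intervention". Section 1.1 gives the purpose: "The educational presentation will be recorded and emailed to participants within 1 week of intervention to re-watch/review".
- Follow-up: "Participants will then receive a post-survey 1 month after educational session".

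Section 1.4 keeps the instrument constant: "The pre- and post-intervention survey will be the same, except the post-intervention survey will not include demographic questions". One question about the Zoom moderator is added at the end of the post-survey. Section 2.26 gives the place where procedures are performed: "Online via REDCap Survey and Zoom-based educational intervention". Section 2.21 confirms that there is no control group.

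The respondent wording in section 2.23 asks people to answer according to their actual behaviour and lets them skip questions. It does not mention the recording or any other source. No supervision, time limit or answer-from-memory instruction is described for either survey. The questionnaires are in appendices that are not part of the text available here.

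**The concern.** A pre-post comparison of knowledge is interpretable only if the two measurements are taken under like conditions. Here the study itself changes one condition. It supplies the lesson, which covers the surveyed topics of nutrition, physical activity, screen time and sleep, after the first survey and well before the second. A respondent who opens the recording to answer a factual item is scored as having learned it.

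Any such look-up raises only the post score. There is no comparison group in which the same effect would show, and the plan collects nothing on use of the recording that would allow an adjustment later. A significant knowledge gain could therefore be reported when less was retained than the result suggests.

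**Working it through.** **Timing.** The recording is due by day 7 after the session, and the post-survey is sent at one month, about day 30. 30 − 7 = 23, so the recording is in hand about three weeks or more before the post-survey opens. The pre-survey precedes the session, so the respondent's own session has not yet been recorded.

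**The plan's own figure.** The only number is the goal of 30 dyads. It cannot be reproduced, because no alpha, power, effect size or SD is stated. The plan gives no figure for look-up.

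**Inputs for an illustration**

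- From the plan: n = 30 pairs (all complete, adolescents or parents analysed separately) and a paired t-test.
- Assumed: two-sided 5% level, pre-post correlation r = 0.5, no true gain, a share f = 10% to 40% consulting the recording while answering, and a gain g = 0.5 to 1.0 SD for each who does.

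**Formulas**

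- SD of the change without look-up: √(2(1 − r)) = √(2 × 0.5) = 1.00 SD. Standard error: 1.00/√30 = 0.183 SD.
- Mean bias: f × g, from 0.10 × 0.5 = 0.05 SD to 0.40 × 1.0 = 0.40 SD.
- SD of the change when only a share look up: √(1 + f(1 − f)g²). At f = 0.4 and g = 1.0 this is √1.24 = 1.114, so the standardised shift is 0.40/1.114 = 0.359.
- Rejection when |t| > 2.045 (29 df), by simulation of the mixture with 400,000 runs per cell.

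| Share looking up | Gain 0.5 SD: bias | Rejects | Gain 1.0 SD: bias | Rejects |
|---|---|---|---|---|
| 10% | 0.05 | 5.8% | 0.10 | 7.9% |
| 20% | 0.10 | 8.1% | 0.20 | 16.3% |
| 30% | 0.15 | 12.1% | 0.30 | 30.0% |
| 40% | 0.20 | 17.7% | 0.40 | 47.6% |

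The nominal rate is 5%. Treating the shift as the same for every respondent would give 56.3% at a bias of 0.40 SD. That overstates the case, because look-up by only some respondents also widens the spread of the changes.

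**Sensitivity to the correlation.** At r = 0.7 the SD of the change is √0.6 = 0.775, the standard error is 0.141 SD, and the same mixture rejects in 6.3% (10%, 0.5 SD) to 63.7% (40%, 1.0 SD) of studies.

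**The case against.** **Closed book before, open book after.** A reader might infer this contrast, but the documents do not support it. The pre-survey is equally remote, respondents have two weeks to complete it, and section 1.1 draws the content from public bodies. Look-up is possible at both times. What differs is ready access to the lesson itself. This part of the objection stands in full.

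**The recording is part of the programme.** It is sent for review, so knowledge gained by re-watching before the survey is effect. This also stands. Only consulting it while answering is bias.

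**There may be little to look up.** The survey is adapted from national behaviour and health surveys. Sections 1.4 and 1.6 list items by topic without a knowledge subscale, and self-reported sleep or diet cannot be found in a lecture. The point therefore reaches only items with a factual answer, and the visible text identifies none. The appendix questionnaires might contain such items, or might already carry an instruction. Against this, section 1.4 says that the survey measures knowledge, and Aim 2 depends on it.

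**The motive is weak.** On the stated totals the post-survey has 61 − 7 + 1 = 55 questions for adolescents and 70 − 11 + 1 = 60 for parents. Searching a recording of a 45-minute session while answering is laborious, and the gift card in section 2.7 rewards completion, not correct answers. This makes the low end of the range more plausible, but it does not rule look-up out.

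**Conclusion.** The concern holds in a limited form. The recording is available at the post-survey and not at the pre-survey, and the visible wording asks for no answer from memory. For factual items, look-up while answering can inflate the Aim 2 gain, and the design cannot detect it.

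The size is unknown. Under the stated assumptions (r = 0.5) the false-positive rate runs from about 6%, which is negligible, to just under 48%. The shares, gains, correlation and test level are not from the documents.

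A reader might go further and conclude that the knowledge gain is certainly biased upward, or that every participant holds the recording. Neither follows. Nothing shows that anyone would consult it while answering, and the plan does not say whether people who miss the live session receive it. The case for change rests on the possible direction of the error and the very low cost of reducing it.

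**What to change.** 1. In sections 1.4 to 1.6, and in the respondent wording in section 2.23, place the same line before the knowledge items in both the pre-survey and the post-survey: *Please answer from memory, without looking anything up, including the recording.* To place it, the plan must say which items those are. Using one wording at both times keeps the instruction constant and also discourages use of public sources at baseline.
2. Describe the Aim 2 effect as that of the session plus the emailed recording, since respondents may have had both by the time they are measured.

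Blocking access to the recording while a post-survey is outstanding is not recommended. It would withdraw part of the programme, need handling for each respondent, and leave public sources and notes open.

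The cost is one instruction line and one sentence on the effect, with no new data item. The downside is that the line relies on compliance, so it reduces look-up but does not remove it.
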